18.2 Serious Adverse Events

Emergency contact details for reporting of serious adverse events are included in the CIP (Appendix A5).

Serious Adverse Events are adverse events that:

- a) led to a death,
- b) led to a serious deterioration in health that either:
 - 1) resulted in a life-threatening illness or injury, or
 - 2) resulted in a permanent impairment of a body structure or a body function, or
 - 3) required in-patient hospitalization or prolongation of existing hospitalization, or
 - 4) resulted in medical or surgical intervention to prevent life threatening illness or injury or permanent impairment to a body structure or a body function.
- c) led to fetal distress, fetal death or a congenital abnormality or birth defect.

In case of a serious adverse event and subsequent need for un-blinding the name-code list can be assessed immediately and breaking the code will not cause any further problem. The data recorded until the report of adverse event will remain included in the dataset.

18.3 Report by the investigator to the sponsor

DMG has implemented and maintains a system to ensure that the reporting of the reportable events will be provided by the investigator to the sponsor in acceptable timely conditions using the Adverse Event/ Adverse Device Effect (AE/ADE) Report Form (Appendix A6).

18.4 Report by the sponsor to the National Competent Authorities

Reportable events will be reported at the same time to all National Competent Authorities where the clinical investigation has commenced.

- a SAE which indicates an imminent risk of death, serious injury, or serious illness and that requires prompt remedial action for other patients/subjects, users or other persons or a new finding to it: immediately, but not later than **2 calendar** days after awareness by sponsor of a new reportable event or of new information in relation with an already reported event.
- any other reportable events or a new finding/update to it: immediately, but not later than **7 calendar** days following the date of awareness by the sponsor of the new reportable event or of new information in relation with an already reported event.

19 Early Termination or Suspension of the Investigation

All materials and devices used in this study have been approved by local regulatory bodies and are currently on the market in various parts of the world. Their clinical use in this investigation is according to label. Therefore, early termination or suspension of the investigation due to problems with the restorative materials is not anticipated.

If the investigation is terminated prematurely or suspended, the principal clinical investigator will promptly inform the clinical investigators of the termination or suspension and the reason(s) for this.

The IRB will also be informed promptly and provided with the reason(s) for the termination or suspension by the principal clinical investigator.

20 Publication Policy

Publication of (parts of) the trial by the Research Team will take place only with the written consent of the Sponsor, or following a period of one year from the date the Sponsor receives the related report.

21 Administrative Arrangements

21.5 Projected Time Frame

The clinical study will start as soon as the required ethical approvals have been received and Training has been provided to the clinical team. [REDACTED]

The time frame is summarized in table 22.5

Table 22.5 Overview of the study's time frame

[REDACTED]
[REDACTED]

time	Study part
[REDACTED]	Study preparation – CIP and IRBs completed
[REDACTED]	Training of clinical team
[REDACTED]	Clinical site preparation
[REDACTED]	Clinical study initiation 
- Patient screening and enrollment- Clinical phase: screening and baseline sessions
[REDACTED]	Baseline report
[REDACTED]	Six-month recall
[REDACTED]	Six-month report
[REDACTED]	One-year recall
[REDACTED]	One-year report
[REDACTED]	Two-year recall
[REDACTED]	Two-year report
[REDACTED]	Three-year recall
[REDACTED]	Three-year report
[REDACTED]	Completion of three-year study- Final report

21.6 Financing

Financial agreements regarding funding of the different aspects of the investigation are part of separate contracts between the Sponsor and the Research Team / University of Alabama at Birmingham, Alabama, US.

21.7 Reimbursement to Subjects

Subject compensation and incentives being part of the subject retention package for the clinical site will be part of a separate contract and fall outside the scope of the CIP.

21.8 Insurance of the Subjects

The study materials in this investigation are cleared by the governing bodies of the participating countries (US, Germany). Therefore, the subjects taking part in the trial are insured by the Sponsor against any injury caused by the study materials under investigation. If applicable, additional regulatory requirements in participating countries will be observed and are part of a separate contract.

A previous infiltration study by Martignon et al. [5] reported a 3-year difference of proportions of 37.8% (95%CI: 20.5-55.2%) with (resin infiltration (68%) vs. control (30%)). Based on this and with alfa = 0.05 and a power of 80% the calculated sample size (t-test; matched pairs) would be 23 lesion pairs (thus 23 participants) to find significant differences. However, this study aimed to enroll 150 participants to not only allow for a potentially high attrition rate (20%) over a period of 3 years, but also aiming to better quantify the efficiency of the treatment effect.

Statistical Analysis

All evaluations are performed by two trained and calibrated examiners. The primary outcome is proportion of lesions that required restorative treatment (filling) after 3 years as measured via dental examination. Differences between groups will be tested using Fisher's exact test and ANOVA for Repeated Measures for subgroup analysis based on caries risk. Secondary outcomes are change in categorical lesion depth (progression to next depth category lesion; E1->E2->D1->D2->filling) after 6 months and 1, 2 and 3 years as measured by pairwise comparison of radiographs as well as the influence of Icon treatment on clinical parameters. Differences will be analyzed with McNemar's test with 95% confidence interval (95% CI) and P = .05.

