4.3.4 Clinical Studies

Infiltrating a caries lesion is a strategy to strengthen damaged tooth structure and to reduce caries progression without any surgical intervention.¹⁻³ Management of early lesions by infiltrating instead of or postponing restorative treatment would have a great impact towards improving oral health care by means of its non-invasive nature. It will drastically lengthen the life-cycle of a tooth.³ Infiltration would provide a simple and cost-effective management option with the least possible iatrogenic effect and diminished need for future re-treatment due to deteriorating of restoration margins.⁴

The promising *in vitro* results of caries infiltration on extracted teeth were underlined by different clinical trials. Several groups reported slower caries progression in infiltrated sites compared to controls: Radiographically obtained quantification reveals lesion progression in 16% of infiltrated sites compared to 53% for controls after one year and for 24% (infiltration group) and 62% (control) after two years. Recently, the three year follow-up data were published, reporting 32% progression for infiltrated lesion and 70% for controls in this split-mouth study.⁵ Meyer-Lueckel et al. measured progression rates of 7% (infiltrated sites) and 37% (controls) after 18 month in young adults.⁶ The currently available 3-year data of this study report 4% progression in infiltrated lesion and 42% for controls.⁷ Ekstrand et al. aimed to assess the efficacy of resin-infiltrated lesions covered by fluoride varnish (FV) versus FV treatment only of proximal lesions on deciduous molar teeth in a one year

split-mouth study. Radiographically, 23% of the test lesions and 62% of the control lesions had progressed, comparable to the aforementioned results in young adults.⁸

5 Device Risk Analysis and Assessment

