6.4 Study Overview

To confirm or reject the hypotheses a prospective, double-blind, randomized controlled trial (RCT) is designed to investigate the clinical performance of resin-infiltration as early caries management in a caries-prone population.

This CIP describes a three-year longitudinal, prospective, randomized controlled trial in split mouth design. The study includes a clinical team involving one on-site Principal Investigator (Site-PI)/operator and one back-up Clinical Investigator (CI)/operator.

The clinical site will enroll 150 subjects (in the age range of 14 years or older) with 2 study lesions. If the lesion management provided in the study appears to be insufficient within the investigated period, the study will provide a maximum of 2 traditional restorations for free to participants. The patients will be evaluated at six time points over a period of 3 years. Lesion status and caries risk will be monitored at 6-month intervals, while radiographic evaluation will be conducted at 12-month intervals at 1-, 2- and 3-year recall visits.

7 Design of the Clinical Investigation

The study will be designed as a controlled, double blind, randomized, prospective trial with a three year follow-up period regarding to CONSORT²² recommendations as a single-center study to investigate the effect of caries infiltration as an alternative treatment option.

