11.4 Statistical Analysis

11.4.1 Descriptive Statistics

For the digital subtraction procedure, the ANOVA for Repeated Measures, will be used to determine significance between the two groups ($p=.05$). The remaining endpoints will be listed as percentages rather than subjected to statistical analyses.

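### The SAP's only power statement (23 pairs, 80%) is for radiographic non-progression, not for fillings, its primary outcome; the test for fillings is unpaired or unclear, and protocol 11.4.1 indicates no test

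*Combined protocol and SAP*

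**What the plan says.** **Sample size.** The SAP (Sample Size Determination) says a cited infiltration trial "reported a 3-year difference of proportions of 37.8% (95%CI: 20.5-55.2%) with (resin infiltration (68%) vs. control (30"%). From this, with alpha 0.05 and 80% power, "the calculated sample size (t-test; matched pairs) would be 23 lesion pairs (thus 23 participants) to find significant differences". It then explains the enrolment of 150 by a possible 20% attrition and by the wish to quantify the treatment effect better. Protocol 11.2 expects 120 subjects at the three-year recall and gives no power. Protocol 4.3.4 describes the three-year result of the same reference as "reporting 32% progression for infiltrated lesion and 70% for controls in this split-mouth study", in a series introduced as radiographic.

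**Endpoints.** In the SAP (Statistical Analysis), "The primary outcome is proportion of lesions that required restorative treatment (filling) after 3 years as measured via dental examination". Change in radiographic depth category is secondary there. The protocol differs. Section 6.2 lists both fillings (Aim I) and radiographic lesion change (Aim II) as primary endpoints, and 11.4.3 names caries progression status at three years as the outcome variable.

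**Tests.** Directly after the primary outcome the SAP says "Differences between groups will be tested using Fisher's exact test and ANOVA for Repeated Measures for subgroup analysis based on caries risk". After the secondary outcomes it says "Differences will be analyzed with McNemar's test with 95% confidence interval". Protocol 11.4.1 tests digital subtraction by repeated-measures ANOVA and adds: "The remaining endpoints will be listed as percentages rather than subjected to statistical analyses". Yet Aim I (6.2.1) and Hypothesis I (4.2.1) both expect a significantly lower filling rate.

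**Design.** Protocol 6.4: "This CIP describes a three-year longitudinal, prospective, randomized controlled trial in split mouth design".

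**The concern.** The one power statement in the plan sits just above a primary outcome to which it does not apply. Progression and filling are different events under the plan's own rules. Lesions enter at E1, E2 or D1 (protocol 9.2), and any step to the next depth category counts as progression (SAP). Protocol 14.2 ties invasive treatment to spread into the middle or inner third of dentin, and separately provides for treatment of pulpitis. Many lesions could therefore progress without being filled, and the 38-point difference cannot be assumed for fillings.

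Two things are at stake. A reader may take 80% as the power for the primary outcome, when the plan does not say what filling difference 120 pairs could detect. And the primary analysis is not fixed in advance, because the documents leave room for an unpaired test, a paired test or no test of fillings.

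**Working it through.** **1. What the 23 pairs refer to.** 100 − 32 = 68% and 100 − 70 = 30%, so the SAP's rates are non-progression proportions from the reference in protocol 4.3.4. The SAP does not label them so; it follows from the complements.

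**2. Reproducing 23.** Two-sided alpha 0.05 is assumed, since sidedness is not stated. At zero within-pair correlation the SD of the paired difference is √(0.68×0.32 + 0.30×0.70) = 0.654. The normal approximation is n = ((1.960 + 0.842)×0.654/d)². It gives 23.5 for d = 0.378 and 23.2 for d = 0.38. The matched-pairs t-test that the SAP names has 75.5–75.9% power at 23 pairs and needs 26. It reaches 80% at 23 pairs if the correlation is about 0.10. So 23 follows from the non-progression rates, up to rounding or a small unstated correlation. With 120 pairs expected, this detail has no consequence.

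**3. Fillings with 120 pairs.** 150 × 0.80 = 120. The documents give no filling rate and no within-pair correlation (phi), so all values of both below are assumptions. Paired cells: p11 = pc·pt + phi·√(pc(1−pc)·pt(1−pt)), where pc and pt are the control and Icon filling rates. The discordant cells are pc − p11 and pt − p11. McNemar is the exact binomial version, with unconditional power by enumeration. Fisher is applied to the two margins as if they were independent groups of 120, allowing for their actual correlation.

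For 20% versus 10%, the square-root term is √(0.16×0.09) = 0.12:

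| phi | p11 | discordant cells | exact McNemar power | Fisher power |
|---|---|---|---|---|
| 0 | 0.020 | 0.180 / 0.080 | 51% | 52% |
| 0.2 | 0.044 | 0.156 / 0.056 | 60% | 52% |
| 0.4 | 0.068 | 0.132 / 0.032 | 74% | 52% |

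**4. Size under no difference** (20% in both groups, nominal 5%):

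| phi | Fisher | exact McNemar |
|---|---|---|
| 0 | 3.4% | 3.4% |
| 0.2 | 1.8% | 3.1% |
| 0.4 | 0.6% | 3.0% |

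Fisher becomes more conservative as the correlation rises, which is where its power is lost.

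**5. Detectable differences**, exact McNemar, 120 pairs, at least 80% power (rates rounded down to a tenth of a point):

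| assumed control rate | Icon rate, phi 0 | Icon rate, phi 0.2 |
|---|---|---|
| 10% | 1.3% | 1.9% |
| 20% | 6.9% | 8.0% |
| 30% | 14.3% | 15.6% |

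**6. Precision.** Half-width = 1.96 × SD/√120. For 20% versus 10% the variance of the paired difference is 0.16 + 0.09 − 2·phi·0.12. At phi 0 the SD is 0.500 and the half-width 8.9 points; at phi 0.2 the SD is 0.449 and the half-width 8.0 points.

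**The case against.** Several points on the other side stand.

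- **The 23-pair figure does match a protocol primary endpoint.** Radiographic change is Aim II in 6.2, and 11.4.3 treats progression status as the outcome variable. The mismatch is with the SAP's primary outcome only.
- **The Fisher sentence is ambiguous.** The phrase about caries-risk subgroups might govern both tests, leaving no test clearly named for fillings. The closing McNemar sentence might cover all outcomes, in which case fillings already have a paired test. Clearer wording is needed on each of these readings.
- **Enrolment does not rest on 23.** The SAP justifies 150 by attrition and precision. A reader might infer that the trial is underpowered. The documents do not support that: 120 expected pairs far exceed 23, and without filling rates the power for fillings is unknown, not shown to be low.
- **Fisher does no harm to the type I error here.** A reader might infer that ignoring the pairing inflates false positives. In the scenarios with zero or positive correlation the size stays below 5%. At phi 0 McNemar gains nothing (51% versus 52%), and the largest gain needs phi 0.4, for which the documents give no basis. Exact McNemar is itself somewhat conservative.
- **The text of Amendment 2 is not visible.** Section 11.4.1 carries no revision note, so the conflict stands on the current text, with that caveat.

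**Conclusion.** The point holds as an inconsistency of endpoint and test. The 80% statement concerns radiographic non-progression; nothing visible gives the power for fillings. The natural reading gives the primary outcome an unpaired test in a split-mouth trial, and protocol 11.4.1 conflicts with any test of fillings. The 23 might also be read as an arithmetic error, but it reproduces from the SAP's own rates to within rounding.

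Under assumed filling rates of 20% versus 10% and 120 pairs, choosing Fisher over exact McNemar costs nothing at phi 0, about 8 points of power at phi 0.2 (60% versus 52%) and about 22 at phi 0.4 (74% versus 52%). These sizes depend wholly on the assumed rates and correlation. The mislabelled power statement and the unsettled primary test do not depend on them. This should be fixed before analysis, but it does not undermine the trial.

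**What to change.** Keep 150 enrolled.

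1. In the SAP, name McNemar's test, with its version (for example exact), and a paired 95% confidence interval for the difference as the primary analysis of fillings. Limit Fisher's test to any use for which it is really meant, and change protocol 11.4.1 to agree.
2. Reconcile the endpoint hierarchy across protocol 6.2, protocol 11.4.3 and the SAP. Say that 68% and 30% are non-progression proportions, state the within-pair correlation used for the 23 pairs, and do not present that figure as power for fillings.
3. State the power or detectable difference for fillings at 120 pairs under declared assumptions. One form: exact McNemar, phi 0 to 0.2, gives 80% power for a reduction from 10% to 1.3–1.9%, from 20% to 6.9–8.0%, or from 30% to 14.3–15.6%. It gives about 51–60% power for 20% versus 10%, with a 95% half-width of about 8.0–8.9 points.

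The cost is wording in the SAP and the protocol and one named test, with no added patients or visits. The downside is that the stated power will look less favourable for small filling differences, and at zero within-pair correlation exact McNemar is no more powerful than Fisher.

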21.8	Insurance of the Subjects	56
21.9	Confidentiality	56
22	Appendices	57
23	References.....	90

1 Synopsis of the Clinical Investigation

Introduction

Dental caries is the most widespread of all diseases. It causes destruction of tooth structure by dissolving the enamel on the outside of the tooth first and then progressing into the inside of the tooth. While it is possible to use traditional dental fillings to replace diseased tooth structure, it is far better to slow down or reverse the disease process so that no fillings are needed. One of the most difficult places to use preventive or non-surgical treatment is the contact area between teeth. Recently there is evolving interest in using composites to infiltrate enamel and dentin areas that have just begun to be destroyed by caries. The infiltration technique arrests the lesion progression by sealing the porous surface and restores the damage avoiding ongoing acidic damage of tooth structure.

Objective

Assess the clinical efficacy s of using Icon to infiltrate initial lesions below the tooth surfaces that exist on the contact surfaces between posterior teeth as a means of stabilizing diseased tooth structure and arresting further lesion development.

Materials and Methods

One hundred fifty volunteers (14+ years) with two early lesions in posterior teeth will be enrolled into a clinical trial to evaluate the clinical efficacy of infiltrating the lesions as compared to current watch-and-wait approaches that are combined with good oral hygiene and fluoride application. Each subject will have a treated lesion and a control lesion. Only small early lesions without clinical signs of surface cavitation will be selected. The control lesions will be stabilized through a normal preventive regimen, while the treatment lesions will be infiltrated with a resin. Lesion status will be monitored every six months by clinical examination and as well using annual radiographs.

Clinical Significance

Infiltrating a caries lesion is a potential effective strategy to strengthen damaged tooth structure and to reduce caries progression without any surgical intervention.

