9.3 Randomization

A random assignment of the treatment to teeth is based on equal distribution of the two treatments; each subject will receive both a placebo controlled or an Icon resin treatment for the two proximal carious teeth, assigned by beginning with the tooth with the lowest number, the specific procedure applied to each tooth will be determined by selecting from a box containing two choices (A or B) by the clinician doing the procedure. One tooth (the one with the lowest tooth number in the universal numbering system) will receive the treatment drawn from a box containing the names placebo or Icon. The universal numbering system begins with #1 - the maxillary right third molar and proceeds to #16 the maxillary left molar. In this system the mandibular left third molar is # 17 and the mandibular right third molar is tooth number #32. The treatment (the first one drawn) will be placed on the tooth with the lowest number. The remaining tooth will receive the second treatment. Clinicians and patients

receiving the two treatments will be blinded as to the treatment applied to the specific tooth.

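### The primary outcome (fillings) is tested with Fisher's exact test, which ignores the split-mouth pairing; a paired test is needed

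*Combined protocol and SAP*

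**What the plan says.** The design is paired throughout. The Synopsis states: "Each subject will have a treated lesion and a control lesion". Protocol 6.4 describes a "three-year longitudinal, prospective, randomized controlled trial in split mouth design", and protocol 9.3 allocates within the patient: "each subject will receive both a placebo controlled or an Icon resin treatment for the two proximal carious teeth". The SAP, under Sample Size Determination, uses a matched-pairs t-test and counts lesion pairs.

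Under Statistical Analysis the SAP then says "The primary outcome is proportion of lesions that required restorative treatment (filling) after 3 years", judged at dental examination. The next sentence is "Differences between groups will be tested using Fisher's exact test and ANOVA for Repeated Measures for subgroup analysis based on caries risk". The secondary outcomes follow (change in radiographic depth category and clinical parameters), and after them "Differences will be analyzed with McNemar's test with 95% confidence interval (95% CI) and P = .05".

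Protocol 11.4.1 differs again. It plans repeated-measures ANOVA for digital subtraction and only percentages, with no test, for the other endpoints.

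**The concern.** Fisher's exact test sees only the two totals: how many control lesions and how many infiltrated lesions were filled. It cannot use the fact that each control lesion has a partner in the same mouth. The two lesions share saliva, diet and hygiene, so their outcomes are likely to be positively correlated. Fisher's test then assigns too much variance to the difference, and its p-value is too large. At stake is a real effect on the primary endpoint being declared non-significant because the test discards the information the split-mouth design was chosen to provide.

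The subgroup method raises a related problem. Read in order, the sentence applies repeated-measures ANOVA to the same yes/no filling outcome, split by caries risk. That is a normal-theory method for continuous data and is doubtful when a subgroup has few fillings. The SAP also mentions no treatment-by-risk interaction.

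**Working it through.** **Inputs from the documents.** Alpha 0.05 and power 80% (SAP; two-sided assumed, since sidedness is not stated). Planning proportions 68% and 30%, difference 37.8 points, 23 pairs (SAP). Expected pairs at 3 years: 150 less 20% = 120 (protocol 11.2).

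**Assumed.** Filling rates and the within-patient correlation phi, neither of which the documents give.

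**The plan's own figure.** n = (1.960 + 0.842)² × V / d², with V = p1(1−p1) + p2(1−p2) − 2·phi·√[p1(1−p1)·p2(1−p2)].
- phi = 0: V = 0.2176 + 0.2100 = 0.4276; n = 7.849 × 0.4276 / 0.378² = 23.5, so 24 pairs.
- phi = 0.05: V = 0.4276 − 0.0214 = 0.4062; n = 22.3, so 23 pairs.

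The stated 23 is thus reproduced as a paired calculation with correlation near zero. The 68% and 30% are the complements of the 32% and 70% radiographic progression in protocol 4.3.4, so they are not filling rates.

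**Why Fisher's test is conservative here.** With a common rate p, the true variance of the difference is 2p(1−p)(1−phi)/n, while an independent-samples test works as if phi were 0. At phi = 0.4 the true standard error is √0.6 = 0.775 of the assumed one. A nominal 1.96 then corresponds to 1.96/0.775 = 2.53, a two-sided level of about 1.1%. The discreteness of the exact test lowers it further.

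**Rejection rates at 120 pairs.** The joint probabilities follow from the two rates and phi: both filled = p1·p2 + phi·√[p1(1−p1)·p2(1−p2)]. Multinomial probabilities were summed over all outcomes with p ≤ 0.05, two-sided.

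| Assumed filling rates (control vs Icon) | Test | phi 0 | phi 0.2 | phi 0.4 | phi 0.6 |
|---|---|---|---|---|---|
| 20% vs 20% (type I error) | Fisher | 3.36% | 1.77% | 0.63% | 0.09% |
| | Exact McNemar | 3.41% | 3.10% | 2.95% | 2.76% |
| 20% vs 10% (power) | Fisher | 51.6% | 51.7% | 51.8% | 51.6% |
| | Exact McNemar | 50.8% | 60.3% | 74.4% | 92.2% |
| 10% vs 4% (power) | Fisher | 34.1% | 32.2% | 29.5% | 25.3% |
| | Exact McNemar | 35.6% | 42.2% | 53.0% | 71.7% |
| 20% vs 5% (power) | Fisher | 93.5% | 95.5% | 97.7% | not possible |
| | Exact McNemar | 93.2% | 97.5% | 99.8% | not possible |

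**Worked example (hypothetical counts).** 120 pairs, 24 control and 13 Icon fillings, both lesions filled in 10 patients. The discordant pairs are 24 − 10 = 14 and 13 − 10 = 3.
- Fisher on 24/120 vs 13/120: p = 0.073.
- Exact McNemar: 2 × (1 + 17 + 136 + 680)/2¹⁷ = 1668/131072, so p = 0.013.
- Standard error of the 9.2-point difference: √[(0.1600 + 0.0966)/120] = 4.6 points if treated as independent; √[(17/120 − 0.0917²)/120] = 3.3 points if paired.

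The phi in this example is (10/120 − 0.200 × 0.1083)/√(0.1600 × 0.0966) = 0.50.

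**Same margins, different pairing.** With 36 vs 24 fillings, Fisher gives p = 0.101 whatever the pairing. Exact McNemar gives 0.043 for 21 vs 9 discordant pairs (phi 0.35) and 0.012 for 16 vs 4 (phi 0.58).

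**The case against.** The strongest reply is that the error runs in the safe direction and may be small. Much of this stands.

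- With positive correlation Fisher's test creates no extra false positives, so a significant result would be credible. The cost is power. Exact McNemar is itself below 5%, at about 3%.
- The loss depends on assumptions. The SAP's 23 pairs imply a correlation near 0.05 on the normal approximation, or 0.10 to 0.15 with the noncentral t. At phi 0.05 to 0.10, power for 20% vs 10% is about 52% with Fisher and 53% to 55% with McNemar. That clue concerns progression, not fillings, and is only indicative.
- For a large effect the choice hardly matters: at 20% vs 5% both tests exceed 93%, and at 70% vs 32% both are near 100%.
- Phi 0.6 is close to the maximum for 20% vs 10%, which is (0.10 − 0.02)/(0.4 × 0.3) = 0.67. It leaves only 0.8% of patients with an Icon-only filling, so the 92% is an upper-end figure.
- The quoted sentence can be read with both methods serving only the subgroup and McNemar covering everything. It also does not name the outcome for the ANOVA, which protocol 11.4.1 assigns to digital subtraction.
- The SAP plans no interval for the primary outcome, so excess width would arise only if an independent-samples interval were added.

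None of this makes Fisher's test suitable for matched pairs. When the correlation is zero McNemar costs almost nothing (50.8% against 51.6%). On the alternative reading no test is clearly assigned to the primary outcome and an unpaired test remains in the subgroup, so the text still needs correcting.

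**Conclusion.** The concern holds. In the natural order of the text, an independent-samples test is assigned to the primary outcome of a within-patient randomized trial, and the paired test is kept for the secondary outcomes. The consequence is a conservative test with lost power, not inflated false positives. At 120 pairs with assumed rates of 20% and 10%, the loss is nil at phi 0, about 9 points at 0.2, 23 points at 0.4 and 41 points at 0.6. Identical totals can fall on either side of 0.05 depending on the test. These sizes rest on assumed filling rates and correlations.

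The point about repeated-measures ANOVA rests on reasoning from the type of outcome. No error rate was calculated for it, and the SAP should say which outcome it serves.

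**What to change.** In the SAP, under Statistical Analysis:

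1. Replace Fisher's exact test for the primary outcome with the exact or mid-p McNemar test on the patient's lesion pair. State the version and that it is two-sided at 0.05.
2. Report the paired risk difference with a 95% CI built for paired proportions, and the full table of concordant and discordant pairs.
3. State how a pair with only one evaluable lesion is handled.
4. For the caries-risk subgroup, use a paired binary method with a treatment-by-risk interaction: conditional logistic regression or GEE. If fillings are sparse, which would trouble those models too, use an exact comparison of the direction of discordant pairs between risk groups. If repeated-measures ANOVA is meant for digital subtraction, say so.
5. Bring protocol 11.4.1 into line, since it now plans no test for fillings.

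The cost is wording in the SAP and a matching sentence in the protocol. No new data or visits are needed, and McNemar's test is already in the plan. The change should be made before treatment codes are linked to outcomes.
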